11.3 Definitions

Adverse Event (AE): Any untoward or unfavorable medical occurrence in a human subject, that includes any abnormal sign (e.g. abnormal physical exam or laboratory finding), symptom, or disease, temporally associated with the subject's participation in the research, whether or not considered related to the research.

Adverse Reaction (AR): An adverse event that is caused by an investigational agent (drug or biologic).

Suspected Adverse Reaction (SAR): An adverse event for which there is a reasonable possibility that the investigational agent caused the adverse event. 'Reasonable possibility' means that there is evidence to suggest a causal relationship between the drug and the adverse event. A suspected adverse reaction implies a lesser degree of certainty about causality than an adverse reaction, which implies a higher degree of certainty.

Serious adverse event (SAE): Any adverse event that results in one or more of the following outcomes:

- Death
- Life-threatening (i.e. an immediate threat to life) event
- Inpatient hospitalization or prolongation of existing hospitalization
- Persistent or significant incapacity or substantial disruption of the ability to conduct normal life functions
- Congenital anomaly/birth defect
- Medically important event*

*Medical and scientific judgment should be exercised in deciding whether expedited reporting is appropriate in other situations, such as important medical events that may not be immediately life threatening or result in death or hospitalization, but may jeopardize the subject or may require intervention to prevent one of the other outcomes listed above.

Unexpected Adverse Event: An AE is unexpected if it is not listed in the Investigator's Brochure or Package Insert (for marketed products) or is not listed at the specificity or severity that has been observed. It is the responsibility of the IND Sponsor to make this determination.

Serious and Unexpected Suspected Adverse Reaction (SUSAR): A SUSAR is a suspected adverse reaction that is both serious and unexpected.

Unanticipated Problem (UP): Any incident, experience, or outcome that is:

1. Unexpected in terms of nature, severity, or frequency in relation to
 - a. The research risks that are described in the IRB-approved research protocol, informed consent document, Investigator's Brochure, or other study documents; and
 - b. The characteristics of the subject population being studied; and

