12.5 Data and Safety Monitoring Board DSMB

The NIAID Intramural DSMB includes independent experts that do not have direct involvement in the conduct of the study and have no significant conflicts of interests as defined by NIAID policy. The Board will review the study prior to initiation and twice a year thereafter. The Board may convene additional reviews as necessary. The Board will review the study data to evaluate the safety, efficacy, study progress, and conduct of the study. All SAEs, all UPs, and all IND Safety Reports will be reported by the PI to the DSMB at the same time they are submitted to the IRB or IND Sponsor. The PI will notify the DSMB of any cases of intentional or unintentional unblinding as soon as possible. The PI will notify the Board at the time pausing or halting criteria are met and obtain a recommendation concerning continuation, modification, or termination of the study. The PI will submit the written DSMB summary reports with recommendations to the IRB(s).

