12.7 Pausing Rules

If any of the following criteria are met at any time the study will be paused to further enrollment until assessed by the medical monitor:

- Any SAE as defined in Section 11.3 that can be possibly, probably, or definitively attributed to the study drug
- Three or more subjects in the same cohort experiencing the same Grade 2 or higher adverse effect that can be possibly, probably, or definitively attributed to the study drug
- Two or more subjects develop the same or clinically similar Grade 3 AE or laboratory abnormality
- Two or more subjects develop a serum creatinine \geq Grade 2 toxicity (≥ 1.8 mg/dL)
- Two or more subjects develop ≥ 1.5 -fold increase in serum creatinine level from baseline
- Two or more subjects develop GFR < 70 mL/min, irrespective if serum creatinine is normal range or Grade 1
- Two or more subjects develop a serum creatinine \geq Grade 2 toxicity in PT and/or PTT (i.e. one grade 2 PT and one grade 2 PTT would meet this pausing rule)

The medical monitor can request information needed (such as a listing of graded AEs and unblinded randomization scheme (directly from the NIH Clinical Center investigational pharmacy group) to evaluate the data. The sponsor medical monitor will ultimately make the decision to either resume the study, ask for formal DSMB review, or stop the study.

If the trial is stopped due to unacceptable adverse events or stopping criteria, the IRB will be notified.

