12.8 Dose Escalation Rules

When the results from the Day 7 visit for the last subject in a cohort (e.g., Cohort 1) are available safety parameters will be analyzed to determine the overall safety of that dose-level (e.g., 1 mg/kg). If any of the following criteria are met, the corresponding dose-level is not considered “acceptably safe”, and the study will not proceed to the next higher dose group (as the review is blinded, this will be across treatment arms).

- Any SAE that can be possibly, probably, or definitively attributed to the study drug
- Any immediate hypersensitivity or cytokine storm events
- Two or more subjects with asymptomatic positive anti-IgG (rheumatoid factor)
- One or more subjects with positive anti-IgG (rheumatoid factor) with associated rheumatologic symptoms (i.e. arthralgia, myalgia, etc.)

- Two or more subjects across all cohorts experience the same Grade 3 or higher adverse effect that can be possibly, probably, or definitively attributed to the study drug
- Three of the first 10 subjects (30%) experience the same grade 2 or higher adverse effect that can be possibly, probably, or definitively attributed to the study drug or any time thereafter 30% of enrolled subjects have the same grade 2 or higher ‘related’ AE.
- Two or more subjects across cohorts develop a serum creatinine \geq Grade 2 toxicity (≥ 1.8 mg/dL) or doubled from baseline (whichever is lower)

If any of the above criteria are met at any time, then the DSMB will meet to evaluate unblinded study data and make a determination about continuation of the study and/or amendment of the protocol.

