12.9 Statistical Considerations

12.9.1 Study Size

It is anticipated that in this study the rate of AEs will be very low in general. In particular, we believe that the chance of experiencing any SAE is less than 1%, while the probability of having any Grade 2 AE is less than 20% and is increasingly less common with more severe AEs. Using the binomial distribution function, Table 5 summarizes the probabilities of observing at least one and at least two subjects having an AE given different AE rates. With the planned sample size, the probability of observing at least one subject with an SAE is 0.08 in the largest cohorts (5 and 6) if the SAE rate is 1%. Therefore, we are unlikely to detect SAEs with such low probability of occurrence. On the other hand, for AEs with 20% probability, we have a good chance of observing at least one AE, and that probability is 0.36 in cohorts 1 and 2, 0.59 in cohorts 3 and 4, and 0.83 in cohorts 5 and 6 (target dose), if the rate of the adverse event is 20%.

The probability of observing an AE in one or two subjects per cohort (N receiving SAB are noted) stratified by the true AE rate is as follows:

Table 5: Adverse Event Rate Table

True AE rate	N=2		N=4		N=8	
	>=1	>=2	>=1	>=2	>=1	>=2
0.01	0.02	0.00	0.04	0.00	0.08	0.00
0.05	0.10	0.00	0.19	0.01	0.34	0.06
0.1	0.19	0.01	0.34	0.05	0.57	0.19
0.15	0.28	0.02	0.48	0.11	0.73	0.34
0.2	0.36	0.04	0.59	0.18	0.83	0.50
0.25	0.44	0.06	0.68	0.26	0.90	0.63
0.3	0.51	0.09	0.76	0.35	0.94	0.74
0.35	0.58	0.12	0.82	0.44	0.97	0.83
0.4	0.64	0.16	0.87	0.52	0.98	0.89
0.45	0.70	0.20	0.91	0.61	0.99	0.94
0.5	0.75	0.25	0.94	0.69	1.00	0.96
0.55	0.80	0.30	0.96	0.76	1.00	0.98
0.6	0.84	0.36	0.97	0.82	1.00	0.99
0.65	0.88	0.42	0.98	0.87	1.00	1.00
0.7	0.91	0.49	0.99	0.92	1.00	1.00
0.75	0.94	0.56	1.00	0.95	1.00	1.00
0.8	0.96	0.64	1.00	0.97	1.00	1.00
0.85	0.98	0.72	1.00	0.99	1.00	1.00
0.9	0.99	0.81	1.00	1.00	1.00	1.00
0.95	1.00	0.90	1.00	1.00	1.00	1.00

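### The Section 12.7 pausing criterion for two similar Grade 3 events omits 'or higher', so read literally it does not count Grade 4 events

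*Combined protocol and SAP*

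**What the plan says.** Section 12.7 lists criteria that pause enrollment until the medical monitor has assessed them. The third reads "Two or more subjects develop the same or clinically similar Grade 3 AE or laboratory abnormality". It carries no attribution condition and is not limited to one cohort.

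Other graded thresholds are open-ended. The second bullet of the same list begins "Three or more subjects in the same cohort experiencing the same Grade 2 or higher adverse effect" and requires attribution to study drug. The creatinine and PT/PTT bullets use a 'greater than or equal to' sign with Grade 2. In Section 12.8 the parallel escalation rule begins "Two or more subjects across all cohorts experience the same Grade 3 or higher adverse effect", again with attribution. Exclusion criteria 8 and 9 in Section 4.4 refer to Grade 3 or greater.

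Meeting a pausing criterion has a second consequence, in Section 12.5: "The PI will notify the Board at the time pausing or halting criteria are met and obtain a recommendation".

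**The concern.** The protocol marks its thresholds as open-ended wherever it means them to be, so a bullet that says only Grade 3 can be read as excluding Grade 4. Followed to the letter, the rule would pause for two Grade 3 liver enzyme elevations but not for two at Grade 4.

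This bullet matters more than its neighbors because it is the only general trigger in 12.7 that does not depend on a causality judgment. The other triggers without attribution cover only creatinine, GFR and PT/PTT. For the remaining safety laboratory tests in Section 7.1.1 (transaminases, bilirubin, LDH, CPK, blood counts), it is the only pausing rule that does not rest on a blinded attribution in a first-in-human product.

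If the trigger is missed, the Section 12.5 duty to go to the DSMB is missed with it. A non-serious cluster judged unrelated would then have no stated automatic route to the Board before its twice-yearly review, unless it was also an unanticipated problem.

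**Working it through.** **Which pairs of events escape.** Take two subjects with the same event, at least one at Grade 4 and fewer than two at Grade 3. The literal third bullet is not met. The other rules then apply as follows.

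- *Related SAE (12.7, first bullet).* One is enough to pause, but it must be both serious and attributed. Section 11.3 defines seriousness by outcome ("Any adverse event that results in one or more of the following outcomes"), so a Grade 4 laboratory value is not an SAE by its grade alone.
- *Three attributed Grade 2 or higher events in one cohort (12.7).* Needs a third subject, a single cohort and attribution.
- *Creatinine, GFR and PT/PTT bullets (12.7).* These cover pairs at any higher grade without attribution, for those parameters only.
- *Two attributed Grade 3 or higher events (12.8).* Blocks escalation ("the study will not proceed to the next higher dose group") and brings an unblinded DSMB review at any time, but needs attribution.
- *SAE reporting (12.5).* "All SAEs, all UPs, and all IND Safety Reports will be reported by the PI to the DSMB", whatever the attribution. Non-serious Grade 4 values are not covered unless they are unanticipated problems.
- *Investigator discretion (12.2.1).* Permitted, not required.

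What remains is mainly a pair judged unrelated or non-serious, outside renal function and coagulation.

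**Size before backstops.** The documents give no Grade 3 or Grade 4 rate. Section 12.9.1 says only that "the probability of having any Grade 2 AE is less than 20% and is increasingly less common with more severe AEs". All rates below are therefore assumptions. As a check on the method, the exact binomial reproduces the Table 5 rows tested; for example, N=8 at a rate of 0.20 gives 0.832 and 0.497 against the printed 0.83 and 0.50.

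Let p be the true rate of one Grade 3–4 event, q the share of those events at Grade 4, and n = 2+2+4+4+8+8 = 28 SAB-301 recipients (Table 1).

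- Intended trigger: P(X ≥ 2), X ~ Bin(n, p)
- Literal trigger: P(Y ≥ 2), Y ~ Bin(n, p(1−q))
- Loss: the difference

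Worked case, p = 0.05 and q = 0.3: intended = 1 − 0.95^28 − 28(0.05)(0.95^27) = 0.4117. The literal rate is 0.05 × 0.7 = 0.035, which gives 0.2567. The loss is 0.1550.

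| p | Intended | Literal, q = 0.1 / 0.2 / 0.3 | Loss, q = 0.1 / 0.2 / 0.3 |
|---|---|---|---|
| 0.01 | 0.0318 | 0.0262 / 0.0211 / 0.0164 | 0.0056 / 0.0107 / 0.0154 |
| 0.02 | 0.1075 | 0.0900 / 0.0736 / 0.0583 | 0.0174 / 0.0339 / 0.0492 |
| 0.05 | 0.4117 | 0.3611 / 0.3091 / 0.2567 | 0.0506 / 0.1025 / 0.1550 |

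If the bullet were counted within each cohort, the trigger probability would be 1 − ∏P(X ≤ 1) over the six cohorts, and the loss runs from 0.0013 (p = 0.01, q = 0.1) to 0.0661 (p = 0.05, q = 0.3). Over all 38 subjects at the same rates, it runs from 0.0095 to 0.1870.

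**Size after the two main backstops (n = 28).** Split events independently into Grade 3 or 4 and related or unrelated, with a related share of 0.5 and every related Grade 4 event counted as an SAE. The escaping probability is that of at least two events, fewer than two at Grade 3, fewer than two related, and no related Grade 4.

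| p | q = 0.1 | q = 0.3 |
|---|---|---|
| 0.01 | 0.0027 | 0.0069 |
| 0.05 | 0.0238 | 0.0640 |

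**The case against.** The strongest reply is that this is an editorial slip with an obvious intent. Section 12.8 shows what was meant, and harm follows only if the investigator and medical monitor treat two Grade 4 events as less alarming than two Grade 3 events. That stands as a comment on likelihood: the figures describe the literal reading and are not an expected loss. It does not defend the wording, since a mandatory pause should not depend on a charitable reading.

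Several points fairly shrink the size.

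- The upper figures need 5% × 30% = 1.5% of recipients to have one specific Grade 4 event. Section 12.9.1 expects less than 1% for any SAE. Not every Grade 4 event is an SAE, so this is no contradiction, but it is the pessimistic end. At rates of 2% or less, the net loss is at most 0.022.
- The related share of 0.5 is arbitrary, and the threshold for possible relatedness in Section 11.1.1 is low. At 0.8, also assumed, the net range falls to 0.001–0.023. If half the unrelated Grade 4 events are also SAEs, it falls to about 0.0005–0.011.
- A subject whose laboratory value is Grade 4 at one visit and Grade 3 at another counts literally. The model ignores this.
- Some 12.8 criteria (hypersensitivity or cytokine storm, rheumatoid factor, creatinine) need no attribution. Safety parameters are reviewed at Day 7 before each escalation, and the Board may convene extra reviews.
- Once cohort 6 is fully dosed there is no enrollment left to pause. The pooled figures include pairs completed after that point, when only the DSMB notification would remain.

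None of these supplies the missing words.

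**Conclusion.** The concern holds. As written, the third pausing criterion does not count Grade 4 events, and no other text in the protocol corrects it. It should be changed.

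The gap is narrow. For 28 recipients, the loss in trigger probability before backstops is 0.006–0.015 at a 1% event rate, 0.017–0.049 at 2% and 0.051–0.155 at 5%, with 10% to 30% of events at Grade 4. After the related-SAE pause and the 12.8 rule it is about 0.003–0.064 if half the events are judged related, and smaller if more are. Every rate and share is assumed. The conclusion rests on the comparison of the texts and not on these figures.

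A separate wording slip in the last 12.7 bullet is worth correcting at the same time: it names serum creatinine where it means PT and/or PTT. Its own bracketed example makes the intent clear, so no change in trigger probability is claimed. It is, however, the only coagulation-specific trigger in 12.7 or 12.8, and Section 8.1.1 relies on serial PT/PTT to watch for a named bovine-protein risk.

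**What to change.** In the third bullet of Section 12.7, insert *or higher* after *Grade 3*, so that the criterion covers two or more subjects with the same or a clinically similar adverse event or laboratory abnormality at Grade 3 or above. Leave it free of any attribution condition.

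In the last bullet, delete *a serum creatinine*, so that the trigger is two or more subjects with Grade 2 or higher toxicity in PT and/or PTT, as its example already implies.

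The cost is two words added and three deleted. No samples, subjects or time are added. Slightly more pauses are possible, but only for clusters that include a Grade 4 event.

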12.8 Dose Escalation Rules

When the results from the Day 7 visit for the last subject in a cohort (e.g., Cohort 1) are available safety parameters will be analyzed to determine the overall safety of that dose-level (e.g., 1 mg/kg). If any of the following criteria are met, the corresponding dose-level is not considered “acceptably safe”, and the study will not proceed to the next higher dose group (as the review is blinded, this will be across treatment arms).

- Any SAE that can be possibly, probably, or definitively attributed to the study drug
- Any immediate hypersensitivity or cytokine storm events
- Two or more subjects with asymptomatic positive anti-IgG (rheumatoid factor)
- One or more subjects with positive anti-IgG (rheumatoid factor) with associated rheumatologic symptoms (i.e. arthralgia, myalgia, etc.)

- Two or more subjects across all cohorts experience the same Grade 3 or higher adverse effect that can be possibly, probably, or definitively attributed to the study drug
- Three of the first 10 subjects (30%) experience the same grade 2 or higher adverse effect that can be possibly, probably, or definitively attributed to the study drug or any time thereafter 30% of enrolled subjects have the same grade 2 or higher ‘related’ AE.
- Two or more subjects across cohorts develop a serum creatinine \geq Grade 2 toxicity (≥ 1.8 mg/dL) or doubled from baseline (whichever is lower)

If any of the above criteria are met at any time, then the DSMB will meet to evaluate unblinded study data and make a determination about continuation of the study and/or amendment of the protocol.

12.9 Statistical Considerations

12.9.1 Study Size

It is anticipated that in this study the rate of AEs will be very low in general. In particular, we believe that the chance of experiencing any SAE is less than 1%, while the probability of having any Grade 2 AE is less than 20% and is increasingly less common with more severe AEs. Using the binomial distribution function, Table 5 summarizes the probabilities of observing at least one and at least two subjects having an AE given different AE rates. With the planned sample size, the probability of observing at least one subject with an SAE is 0.08 in the largest cohorts (5 and 6) if the SAE rate is 1%. Therefore, we are unlikely to detect SAEs with such low probability of occurrence. On the other hand, for AEs with 20% probability, we have a good chance of observing at least one AE, and that probability is 0.36 in cohorts 1 and 2, 0.59 in cohorts 3 and 4, and 0.83 in cohorts 5 and 6 (target dose), if the rate of the adverse event is 20%.

The probability of observing an AE in one or two subjects per cohort (N receiving SAB are noted) stratified by the true AE rate is as follows:

Table 5: Adverse Event Rate Table

True AE rate	N=2		N=4		N=8	
	>=1	>=2	>=1	>=2	>=1	>=2
0.01	0.02	0.00	0.04	0.00	0.08	0.00
0.05	0.10	0.00	0.19	0.01	0.34	0.06
0.1	0.19	0.01	0.34	0.05	0.57	0.19
0.15	0.28	0.02	0.48	0.11	0.73	0.34
0.2	0.36	0.04	0.59	0.18	0.83	0.50
0.25	0.44	0.06	0.68	0.26	0.90	0.63
0.3	0.51	0.09	0.76	0.35	0.94	0.74
0.35	0.58	0.12	0.82	0.44	0.97	0.83
0.4	0.64	0.16	0.87	0.52	0.98	0.89
0.45	0.70	0.20	0.91	0.61	0.99	0.94
0.5	0.75	0.25	0.94	0.69	1.00	0.96
0.55	0.80	0.30	0.96	0.76	1.00	0.98
0.6	0.84	0.36	0.97	0.82	1.00	0.99
0.65	0.88	0.42	0.98	0.87	1.00	1.00
0.7	0.91	0.49	0.99	0.92	1.00	1.00
0.75	0.94	0.56	1.00	0.95	1.00	1.00
0.8	0.96	0.64	1.00	0.97	1.00	1.00
0.85	0.98	0.72	1.00	0.99	1.00	1.00
0.9	0.99	0.81	1.00	1.00	1.00	1.00
0.95	1.00	0.90	1.00	1.00	1.00	1.00

12.10 Study Endpoints

12.10.1 Primary Endpoint

- Type and frequency of AEs experienced by subjects receiving SAB-301 at escalating dose-levels, as compared to placebo

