Secondary Objectives:

- To evaluate the pharmacokinetics of intravenously administered SAB-301 in healthy adults, following single intravenous administration at escalating dose-levels
- To determine the ability of serum levels of SAB-301 to neutralize Middle East Respiratory Syndrome (MERS) virus
- To evaluate the immunogenicity of SAB-301

Primary Endpoint: Type and frequency of adverse events experienced by subjects receiving SAB-301 at escalating dose-levels, as compared to control saline

Secondary Endpoints:

- Pharmacokinetic profile of intravenously administered SAB-301 in healthy adults
- MERS virus neutralization assay
- Frequency and concentrations of antibodies caused by SAB-301, as measured by:
 - Anti-IgG antibodies using rheumatoid factor
 - Anti-SAB-301
 - Anti-Bovine Kappa light chain
 - Anti-██████████ Antibody

PRÉCIS

The administration of convalescent plasma or hyperimmune immunoglobulin is often used for treatment of emerging infectious diseases. However, production of large quantities of anti-pathogen human plasma and/or immunoglobulin with high affinity and avidity antibodies currently requires donations by convalescent humans, a process that can limit availability for a number of reasons. One novel alternative source is transchromosomal (Tc) cattle that produce fully human polyclonal IgG (hIgG) de novo and mount a robust antibody immune response after vaccination.

This study will evaluate the safety, tolerability, and immunogenicity of SAB-301, a fully human polyclonal anti-MERS IgG collected from transchromosomal cattle. Beginning with a low single-dose, subjects are randomized to receive either SAB-301 or a normal saline control, and evaluated on Study Days 1, 3, 7, 21, 42, and 90. The safety and tolerability is evaluated using symptoms, clinical laboratory tests, pharmacokinetics, and immunogenicity assays. Utilizing a series of stopping rules and a medical monitor, the dose will be escalated as safety and tolerability are established.

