3 INVESTIGATIONAL PLAN

3.1 General

Study size: 38 subjects (up to 70 subjects screened to randomize a total of 38 subjects)

Study duration: 1 year

Study duration of individual subjects (not including screening): 90 days

Sex distribution: males and females

Age range: 18 to 60 years

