3.2 Study Design

This safety and tolerability study of intravenous (IV) SAB-301 consists of up to 6 single dose-levels or cohorts (cohort 1–6) in a double-blind, randomized, placebo-controlled dose-escalating cohort design. Six cohorts of 3-10 subjects each will be administered a single IV dose of SAB-301 or saline placebo. At very low doses, the concern is primary allergic or T-cell activation/cytokine storm, so small cohort sizes can be utilized. As the target dose is approached, the sample size will increase to increase the likelihood of detecting toxicity events. The cohorts and dose levels are outlined in [Table 1](#).

Table 1: Cohorts and Dose Levels

Cohort	Number of Subjects receiving SAB-301						Number of Subjects receiving Saline Control			
	1.0 mg/kg	2.5 mg/kg	5 mg/kg	10 mg/kg	20 mg/kg	50 mg/kg				
1	2						1			
2		2						1		
3			4						2	
4				4					2	
5					8					2
6						8				2

The administration of the study drug will occur in the day-hospital at the NIH Clinical Center. The number of subjects dosed will follow the limitations below:

- For the first cohort, no more than 1 subject will be dosed on each day.
- For the second cohort, no more than 2 subjects will be dosed on each day.
- For cohort 3-4, no more than 3 subjects will be dosed on each day.
- For cohort 5-6, no more than 3 subjects will be dosed on each day and no more than 6 subjects will be dosed per week.

Beginning with a low single-dose, subjects are randomized to receive either SAB-301 or placebo on Day 0. Subjects are then evaluated on Study Days 1, 3, 7, 21, 42, and 90.

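### Does the comparison with saline fail because each dose level has only one or two saline subjects and Section 12.9 describes no comparison?

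*Combined protocol and SAP*

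**What the plan says.** The endpoint in Section 12.10.1 is "Type and frequency of AEs experienced by subjects receiving SAB-301 at escalating dose-levels, as compared to placebo". The Protocol Summary gives the same endpoint with saline named as the comparator: "Type and frequency of adverse events experienced by subjects receiving SAB-301 at escalating dose-levels, as compared to control saline". Neither version says whether the comparator is the saline subjects of the same cohort or all of them.

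Section 3.2 sets the structure: "Six cohorts of 3-10 subjects each will be administered a single IV dose of SAB-301 or saline placebo". Table 1 assigns 2, 2, 4, 4, 8 and 8 subjects to SAB-301 and 1, 1, 2, 2, 2 and 2 to saline. The total agrees with Section 3.1: "Study size: 38 subjects (up to 70 subjects screened to randomize a total of 38 subjects".

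Section 12.9 has one subsection, 12.9.1 Study Size. Its Table 5 concerns active recipients only: "The probability of observing an AE in one or two subjects per cohort (N receiving SAB are noted". For an AE with a true rate of 20%, the text says "we have a good chance of observing at least one AE, and that probability is 0.36 in cohorts 1 and 2", and the same sentence goes on to give 0.59 for cohorts 3 and 4 and 0.83 for cohorts 5 and 6. No section states a comparative test, a significance level, a saline AE rate or an interval method.

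**The concern.** The endpoint is worded as a comparison and ten people are randomised, blinded, to saline, yet the only statistical section ignores them. Headache, infusion-site effects and laboratory fluctuation can occur on saline too, so the control group matters for interpretation. Read dose level by dose level, the control is one or two people, which says almost nothing about the background rate. If that were the planned analysis, the primary endpoint could not be answered in most cohorts, and a sentence requiring pooled saline would seem to repair it without any extra subjects.

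Section 12.9.1 also invites criticism for describing detection favourably and then printing 0.36 for cohorts 1 and 2, where a 20% AE is more likely to be missed than seen.

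**Working it through.** **Inputs.** From Table 1: SAB-301 2 + 2 + 4 + 4 + 8 + 8 = 28; saline 1 + 1 + 2 + 2 + 2 + 2 = 10; total 38. From Section 12.9.1: SAE rate below 1%, Grade 2 AE rate below 20%. Assumed, because the documents give none: Fisher's exact test, two-sided 0.05, and the saline rates shown below.

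**The plan's own figures.** P(at least one AE) = 1 − (1 − p)^n.
- p = 0.20: 1 − 0.8² = 0.360; 1 − 0.8⁴ = 0.590; 1 − 0.8⁸ = 0.832.
- p = 0.01, n = 8: 1 − 0.99⁸ = 0.077.

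These match the printed 0.36, 0.59, 0.83 and 0.08. All of Table 5 reproduces to rounding.

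**Own-cohort comparison.** The smallest attainable p occurs when every active subject and no saline subject is affected. It equals 1/C(n+m, m) for n active and m saline:
- 2 v 1: 1/3 = 0.333
- 4 v 2: 1/15 = 0.067
- 8 v 2: 1/45 = 0.022; the next outcome, 7/8 v 0/2, gives 0.067

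**Pooled saline, 0 of 10 affected.** 2/2 gives p = 0.015, 3/4 gives 0.011 and 4/8 gives 0.023.

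**Precision of the control rate.** With zero events the exact two-sided 95% upper limit is 1 − 0.025^(1/n): 97.5% for n = 1, 84% for n = 2, 31% for n = 10.

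**Power**, by enumerating both binomials and counting only an excess on SAB-301:

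| SAB-301 v saline rate | 8 v 2 | 8 v 10 |
|---|---|---|
| 80% v 10% | 0.14 | 0.84 |
| 60% v 10% | 0.01 | 0.55 |
| 40% v 10% | 0.001 | 0.21 |
| 30% v 10% | 0.000 | 0.09 |
| 20% v 10% | 0.000 | 0.024 |
| 20% v 0% | 0.000 | 0.056 |

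All 28 against 10 at 20% v 10% gives 0.014. The large gains appear only at AE rates far above the plan's expectation. In cohorts 1 to 4 own-cohort power is zero, so a fold-gain is undefined.

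**What pooling assumes.** Saline volume follows the cohort's active volume (Section 5.2.2). Dose divided by concentration in Table 2 gives 1.0, 2.5, 1.25, 2.5, 1.0 and 2.5 mL/kg for cohorts 1 to 6. Cohorts run one after another, each waiting for the Day 7 review of the one before (Section 12.8), so pooled controls are partly non-concurrent. Suppose cohort 6 has no drug effect but a higher background rate than the 10% in the other cohorts' saline subjects. The false-positive rate for 8 v 10 is then 6.3% with a 30% background in cohort 6, and 20.0% with 50%. With 10% throughout it is 0.2%. A listing by cohort offers little protection: comparing cohort 6's 2 saline subjects with the other 8 has power 0.11 to detect 50% against 10%.

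**The case for a change.** The best case for a change is that the comparator really is unstated. Two analysts could follow this document, one using own-cohort saline and the other pooled saline, and describe the background rate very differently: an upper limit of 84% or of 31% after no events. That choice could be made after unblinding. A phase 1 trial need not be powered for a test, but one that doses ten people with saline for comparison can fairly be asked how they will be used, and a sentence would settle it.

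The omission stands as a fact, and neither the escalation rules nor redaction explains it; the Section 12.8 review is blinded and runs across arms. It does not show a wrong analysis, however. Nothing in the plan prescribes own-cohort testing, and in a descriptive dose-escalation study with one or two saline subjects per cohort, showing saline as one column beside the dose levels is the expected summary. A sentence recording this would do no harm, but it would correct no stated rule.

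The other possible changes are weaker. A trend test across doses needs a named AE or grade and a way to handle many AE types; whether to add one is a matter of preference. Quoting 1 − 0.8²⁸ = 0.998 for all recipients assumes the same 20% rate from 1 to 50 mg/kg, whereas Section 3.2 enlarges the later cohorts because toxicity is expected to matter most near the target dose. The favourable wording in Section 12.9.1 is loose for cohorts 1 and 2, but the correct probabilities stand in the same sentence.

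**Conclusion.** No change follows. The plan leaves unwritten how the 10 saline subjects are grouped and how AE incidence is summarised; analysts would fill that gap in the usual way, and the endpoint wording permits it. The stark own-cohort results (smallest p 0.333, 0.067 and 0.022) are correct, but they describe a test the plan never proposes.

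Pooling narrows the zero-event upper limit on the saline rate from 84% with two subjects to 31% with ten. It does not yield a usable test near the rates the plan expects (0.056 at best for 8 v 10 with SAB-301 at 20%), and it carries an assumption of stable background rates that this trial can barely check.

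This rests on reading the endpoint as descriptive. In support, no hypothesis, test or significance level appears anywhere; study size is justified by the chance of observing events; and escalation depends on event counts, not on a contrast with saline. The power figures rest on the assumed test and saline rates given above.
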